In the study **CCI** the Safety population included 182 and 88 patients in reparixin and placebo arm, respectively. Treatment with oral reparixin was well tolerated in terms of TEAEs safety laboratory tests and vital signs parameters. Serious TEAEs were reported in 20 patients (11.0%) in the reparixin group (23 TEAEs) and in 13 (14.8%) in the placebo group (16 TEAEs) and none of these was related to treatment. Ten TEAEs leading to death were reported in 10 patients (5.5%) in the reparixin group and 7 TEAEs leading to death were reported in 7 patients (8.0%) in the placebo group. A total of 13 ADRs were reported in 10 patients (5.5%) in the reparixin group and 11 ADRs were reported in 8 patients (9.1%) in the placebo group on treatment or follow-up period. In summary, treatment with reparixin was associated with lower proportions of patients that reported TEAEs (serious, severe, leading to discontinuation of IMP or having a fatal outcome).

The SOC more frequently (>10%) involved in ADRs observed with oral tablets in COVID-19 pneumonia studies were:

Infections and infestations (about 31% of the overall reported ADRs), including bacterial sepsis, lower respiratory tract infection fungal and pneumonia bacterial.

Gastrointestinal disorders (15%), including abdominal pain upper and diverticulum intestinal haemorrhagic.

Hepatobiliary disorders (15%), including hypertransaminasemia.

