5.3.2. Criteria for permanent discontinuation of the IMP

The IMP must be discontinued in the case:

- Upon initiation of renal replacement therapy;
- Upon increase of ALT and/or AST to ≥ 3 x ULN and total bilirubin > 2 x ULN or upon increase of ALT and/or AST to ≥ 5 x ULN
- The patient is discharged home;
- Withdrawal of informed consent by the patient or his/her legal representative (in this case, the patient / representative will be asked whether they consent to usage of the data already collected in the study; if not, the data will be deleted);
- Pregnancy occurs;
- Development of Serious AE probably or possibly related to IMP, as per PI's judgment;
- Inadvertent missing of 3 or more consecutive doses of the IMP;
- Inability to resolve within 24 hours any medical condition/event that led to temporary withholding of the IMP (see also 5.3.3.);
- Recurrence of AE probably or possibly related to IMP upon re-introduction of the IMP.

Occurrence of renal or hepatic dysfunction will be monitored as part of the biochemistry data set through safety laboratory tests obtained at day 3 ± 8 h, 7 ± 1 , 14 ± 2 , and 21 (if the IMP is meant to be administered up to 21 days). The other criteria that qualify the patient to treatment discontinuation will be monitored daily.

If the IMP administration is prematurely discontinued, the primary reason for discontinuation must be recorded in the eCRF. Patients who discontinue the treatment with the IMP will NOT be withdrawn from the study by default and will be asked to complete safety and efficacy observations as per the protocol unless they withdraw their consent.

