14.4.10. Handling of samples for assays

Local laboratories will perform hematology/biochemistry tests (Safety Laboratory Tests).

CCI [REDACTED] measurement of inflammatory markers (IL-6, IL-8, PAI-1, TNF α , ICAM-1, RAGE) will be performed by a central laboratory selected by Dompe.

All steps will be tracked to ensure correct data reporting.

All samples submitted to these labs will be destroyed after the CSR has been issued or after the patient has withdrawn his/her consent.

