Day 3	1 st IMP intake Date/Time + 36h	1 st IMP intake Date/Time + 59h and 59 min	48h
Day 4	1 st IMP intake Date/Time + 60h	1 st IMP intake Date/Time + 83h and 59 min	72h
Day 5	1 st IMP intake Date/Time + 84h	1 st IMP intake Date/Time + 107h and 59 min	96h
Day 6	1 st IMP intake Date/Time + 108h	1 st IMP intake Date/Time + 131h and 59 min	120h
Day 7	1 st IMP intake Date/Time + 132h	1 st IMP intake Date/Time + 155h and 59 min	144h
Day 8	1 st IMP intake Date/Time + 156h	1 st IMP intake Date/Time + 179h and 59 min	168h
Day 9	1 st IMP intake Date/Time + 180h	1 st IMP intake Date/Time +203h and 59 min	192h
Day 10	1 st IMP intake Date/Time + 204h	1 st IMP intake Date/Time + 227h and 59 min	216h
Day 11	1 st IMP intake Date/Time + 228h	1 st IMP intake Date/Time + 251h and 59 min	240h
Day 12	1 st IMP intake Date/Time + 252h	1 st IMP intake Date/Time + 275h and 59 min	264h
Day 13	1 st IMP intake Date/Time + 276h	1 st IMP intake Date/Time + 299h and 59 min	288h

Standard/Forms/Template				
Title		Statistical Analysis Plan Template		
Code		Version	Effective Date	Page
PPD		01	29 Aug 2022	16 of 78

Day 14	1 st IMP intake Date/Time + 300h	1 st IMP intake Date/Time + 323h and 59 min	312h
--------	---	--	------

Differently from what it was reported in the study protocol, the window used for each day is +/- 12 hours to let each assessment to be unequivocally classified in a given day (not possible by using the time window +/- 8h).

With the exception of Day 1, which covers 12 hours (11 h and 58 minutes), all the other days cover 24 hours (23h and 59 min).

For each endpoint described in section 3.5.1 and 3.5.2, it will be specified whether the study Day will be defined on the basis of Date or Date/time. Section 11.1.1 provides further details with regards to variables derivations based on date or date/time.

Please refer to Table 1: Study Flow Chart for full details on the schedule of suggested assessments.

Notes:

- Study Days will be derived using the algorithms defined above.
- Analysis based on visits (Chest Imaging, labs, ECG ...) will use the assessments collected at that visit, regardless of the study days.

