3.6 Safety endpoints

- Haematology/biochemistry tests change from screening to day 3±8h, 7±1, 14±2, 21±2 (if still receiving reparixin), 28±2 visits and at hospital discharge [by visit]
- eGFR, absolute value and change from screening to day 3±8h, 7±1, 14±2, 21±2 (if still receiving reparixin), 28±2 visits and hospital discharge [by visit]
- Hepatic Function (ALT/AST, total/direct bilirubin), absolute values and change from screening to day 3±8h, 7±1, 14±2, 21±2 (if still receiving reparixin) visits and at hospital discharge [by visit]

Standard/Forms/Template				
Title		Statistical Analysis Plan Template		
Code		Version	Effective Date	Page
PPD		01	29 Aug 2022	23 of 78

- ECG/rhythm analysis changes from screening to day 3 ± 8 h, 7 ± 1 , 14 ± 2 , 21 ± 2 (if still receiving reparixin), 28 ± 2 visits and hospital discharge. [by visit]
- Incidence of secondary infections defined as new (occurring after the first IMP intake) infection in a previously known to be sterile site, including blood, body fluid or tissue, or new pathogen isolated from cultures of biological samples known to be previously infected by day 28 [study day: see section 11.1.1]
- Incidence of TEAEs and TESAEs from the beginning of study treatment to up to the end of study participation.
- Vital Signs change from baseline to daily assessment through extubation (namely, day 1, day 2, day 3, day 7, day 14, day 21) [study day: date/time]

4. Statistical Analysis

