8.2 Clinical laboratory evaluation

Analysis of clinical laboratories data will be performed by treatment for Hematology and Biochemistry (including eGFR) tests. In case of different units of measure considered for the same laboratory

Standard/Forms/Template				
Title		Statistical Analysis Plan Template		
Code		Version	Effective Date	Page
PPD		01	29 Aug 2022	53 of 78

parameter, all values will be converted into Standard International units (if applicable) or to the same unit. Even if laboratory are collected at screening and the protocol mention changes from screening, baseline and changes from baseline will be provided: this means that, if for some reason the screening assessment is done after treatment start date (by mistake or any reason), the value will not be considered in the analysis, since the value will not be flagged as "Baseline" (as defined in section 3.2.2). Subsequent timepoints are Day 3, Day 7, Day 14, Day 21, end of treatment, Day 28 and hospital discharge.

The following summaries will be provided:

- A summary table showing for all laboratory tests the values and changes from baseline to each subsequent visit.
- A summary table showing for all laboratory tests the frequency of the investigator's interpretation at each available visit.
- Shift tables presenting the number and the percentage of patients in each bivariate category (baseline versus each post-baseline visit) with regards to investigator's interpretation.

The following graphical representations will be provided for all laboratory parameters:

- Spaghetti plot of individuals' observed data and change from baseline (with x-axis marked by days relative to start of actual treatment);
- Boxplot for values and changes from baseline by actual treatment at each timepoint.

Listings showing hematology results, biochemistry results, abnormal clinically significant hematology results and abnormal clinically significant biochemistry results will be provided.

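### SAP 8.2 does not count, by arm, the patients who met the protocol's own ALT/AST/bilirubin criterion after first dose

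*SAP*

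**What the plan says.** Protocol 5.3.2 makes a liver finding a mandatory reason for permanent discontinuation. The first limb reads "Upon increase of ALT and/or AST to ≥ 3 x ULN and total bilirubin > 2 x ULN". The same bullet adds a second limb for ALT and/or AST of at least 5x ULN. Both limbs are in multiples of ULN, and the first pairs two analytes in one patient.

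The SAP's liver endpoint (3.6) has a different form: "Hepatic Function (ALT/AST, total/direct bilirubin), absolute values and change from screening to day 3±8h", continuing over the later visits. SAP 8.2 then plans:
- "A summary table showing for all laboratory tests the values and changes from baseline to each subsequent visit";
- counts, visit by visit, of how the investigator classified each result;
- shift tables from baseline, using the same investigator categories;
- spaghetti plots of individual values and changes, and boxplots by visit;
- listings of all biochemistry results and of the clinically significant abnormal ones.

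Units are harmonised, but values are not scaled to a reference range. Protocol 14.4.10 states "Local laboratories will perform hematology/biochemistry tests (Safety Laboratory Tests"), so reference ranges belong to each site. SAP 3.2.1 says that visit-based analyses, laboratory data included, "will use the assessments collected at that visit, regardless of the study days". End of treatment is one of the laboratory timepoints in SAP 8.2.

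**The concern.** The protocol has a definite liver limit, but the laboratory analysis never asks how many patients in each arm reached it. Three features of SAP 8.2 cause this.

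1. A pooled U/L value cannot be read against the limit, because the limit depends on the local ULN.
2. Each visit is summarised separately, so patients who cross at different visits are never added up.
3. ALT/AST and bilirubin are tabulated as separate tests, so the paired limb cannot be read from any table.

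The only categories tabulated are the investigator's interpretation, which is a judgement and not a threshold. Liver injury in a small trial tends to show as a few large values. What is at stake is a safety report that lacks the by-arm count most readers would look for, given that the protocol itself defines the event.

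**Working it through.** The plan gives no figure on this point to reproduce. The check is a reading of every planned output that could carry the criterion, followed by illustrative arithmetic.

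**Where the criterion could appear**

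| Planned output | What it gives | What it misses |
|---|---|---|
| Visit tables (SAP 8.2; statistics in 4.1) | Mean, SD, median, quartiles, minimum, maximum | ULN scaling; per-patient worst value; ALT/AST paired with bilirubin |
| Interpretation and shift tables (SAP 8.2) | Investigator category by visit | Any threshold; an ever-met count |
| Plots and listings (SAP 8.2) | Individual values | ULN scaling; a count by arm |
| IMP discontinuation reasons (SAP 5.3) | By-arm counts, randomized patients | Patients who crossed after drug ended or who stopped for another reason (Protocol 5.3.2 records one primary reason); detail by criterion is not promised |
| TEAE tables (SAP 8.1) | By-arm counts by SOC and PT | Rises not judged clinically relevant (Protocol 8.2); severity is graded by interference with function (Protocol 8.3.3), not by laboratory level |

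The derivation rules in SAP 11.1.1 contain no ULN multiple, no worst post-baseline laboratory value and no joint liver variable.

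**Illustrations**

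From the documents: about 66 patients randomized 1:1, so 33 per arm. Everything else below is assumed.

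*Effect of the local ULN.* Assume that site ULNs for ALT run from 35 to 55 U/L.
- 3x ULN runs from 3 × 35 = 105 to 3 × 55 = 165 U/L.
- 5x ULN runs from 5 × 35 = 175 to 5 × 55 = 275 U/L.
- An ALT of 150 U/L is 150/35 = 4.3x ULN at one site and 150/55 = 2.7x at another. It passes the 3x level at the first and not at the second.

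*Effect of separate visits.* Suppose 3 of 33 patients in an arm each cross at a different visit. Each visit shows at most 1/33 = 3.0%. The ever-met count is 3/33 = 9.1%.

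*Effect on the visit mean.* Assume ALT is lognormal with median 1x ULN and log-SD 0.5.
- Mean = exp(0.5²/2) = 1.133x ULN.
- SD = 1.133 × √(exp(0.25) − 1) = 0.604.
- SE of the between-arm difference = 0.604 × √(2/33) = 0.149.
- One patient at 6x ULN moves the arm mean by (6 − 1.133)/33 = 0.147, or about one SE.

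A single clear case is therefore within ordinary noise in the visit mean.

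*What the count would give.* With the Wilson interval with continuity correction, as SAP 4.1 specifies:
- 3/33: 9.1% (95% CI 2.4 to 25.5).
- 0/33: 0% (95% CI 0 to 13.0).
- For 0/33, the exact one-sided 95% upper bound is 1 − 0.05^(1/33) = 8.7%.
- The chance of seeing at least one case in 33 is 1 − (1 − p)^33, which is 49%, 82% and 97% for true rates of 2%, 5% and 10%.

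**The case against.** A reader might infer that liver toxicity is never counted by arm, or that SAP 8.2 offers only means and opinion. The documents support neither reading.

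- **Other by-arm routes exist.** The criterion is a stopping rule, stopping reasons are tabulated by arm, and the SAP's own definition of a treatment completer uses the specified criterion, so the eCRF records it. TEAEs leading to discontinuation are tabulated as well. These routes are real but incomplete, for the reasons in the table above.
- **Extremes are visible.** Visit maxima, boxplots, individual plots and full listings would show a very high value. They show it in local units, without a count and without pairing to bilirubin.
- **Peaks between visits.** A reader might argue that a peak between day 7 and day 14 drops out and that later visits show only recovery. The documents undercut this. Protocol 5.3.2 monitors the liver through the scheduled safety samples, end of treatment is a tabulated timepoint, and SAP 3.2.3 can remap it to a missing visit. I do not rely on this argument.
- **The prior signal is modest.** Protocol 2.5.2 gives "Hepatobiliary disorders (15%), including hypertransaminasemia", but the 15% is a share of reported reactions, not of patients. If it refers to the 13 reactions on reparixin in the phase 3 COVID-19 study, it is about 0.15 × 13 ≈ 2 events among 182 patients. Protocol 2.6.2.1 reports no important risk identified or suspected. The point rests on the protocol's own criterion, not on an established liver risk.
- **The count would be imprecise.** The intervals for 3/33 and 0/33 overlap, and the two-sided Fisher p-value is 0.24. That is true, but the purpose is to report the event, not to test it.
- **Scale of the issue.** This is a descriptive proof-of-concept trial with a DMC that sees laboratory data, and no planned estimate becomes wrong. That limits the point to a reporting gap.
- **The shells are not available.** SAP 9 places the mock shells in an appendix, so a ULN table there cannot be excluded. If one exists, SAP 8.2 should say so.

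**Conclusion.** The point holds in this form: SAP 8.2 does not derive, or count by arm, the patients who met the Protocol 5.3.2 ALT/AST/bilirubin criterion at any time after first dose. The routes by which the criterion can still surface are partial and depend on a recorded primary reason, a judgement of clinical relevance, or a reader working through unscaled data.

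The gap affects how safety is reported, not any efficacy result. Its size cannot be fixed from the documents, which give neither liver-enzyme variability nor site ULNs. Under the assumptions shown, three cases in one arm could appear as at most 3.0% at any visit when the true ever-met figure is 9.1%, and one patient at 6x ULN shifts a visit mean by about one standard error. The conclusion is conditional on the unseen shells not already containing such a table.

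**What to change.** Add one by-arm table to SAP 8.2, on the SAF set:
- Divide ALT, AST and total bilirubin by the local laboratory ULN.
- Take each patient's worst result after first dose, using every result in the database, including end of treatment.
- Give the number and percentage reaching ALT or AST ≥3x ULN, ALT or AST ≥5x ULN, total bilirubin >2x ULN, and the full Protocol 5.3.2 criterion.
- State how ALT/AST and bilirubin are matched in time for the paired limb, since Protocol 5.3.2 gives no window.
- Show the baseline category alongside. Exclusion criterion 1 applies its enzyme limits only when the Child-Pugh score is unknown, so some patients may enter with raised values.
- Use 95% Wilson intervals with continuity correction, as in SAP 4.1.
- List the patients who meet any limit.

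Keep the existing tables, plots and listings.

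The cost is a paragraph of SAP text, one derived dataset, one table and one listing. Protocol 11.3 already requires each site's normal ranges and their updates. The visible text does not say whether unscheduled results are entered, so the table should use what the database holds and say so.

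There are two downsides. Rises caused by the underlying illness are counted too; the placebo arm and the baseline category help in reading them. And with about 33 patients per arm, even a zero count leaves a rate of up to 8.7% possible (one-sided 95%). This changes reporting only and leaves the clinical stopping rule as it stands.

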8.3 Vital signs

Summary statistics by treatment will be provided along with a summary of the change from baseline at each timepoint for Vital signs:

- Respiration Rate (n/min),
- Heart Rate (beats/min),
- Mean Arterial Pressure (mmHg).

Daily assessments through first extubation will be tabulated (considering Study date based on date/time as per section 3.2.1); all the other assessments after extubation will only be listed.

The following graphical representations will be provided for all quantitative vital signs:

- Spaghetti plot of individuals' observed data and change from baseline (with x-axis marked by days relative to start of actual treatment);

Standard/Forms/Template				
Title		Statistical Analysis Plan Template		
Code		Version	Effective Date	Page
PPD		01	29 Aug 2022	54 of 78

- Boxplot for values and changes from baseline by actual treatment at each timepoint.

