3.3. OVERALL STUDY DESIGN

The study is an international, multicenter, 1:1 randomized, double-blind, placebo-controlled, phase II proof-of-concept trial. It will enroll approximately 66 adult patients hospitalized with ARDS that meet the inclusion criteria, randomly assigned at 1:1 ratio to receive either reparixin 1200 mg (treatment group) through a nasogastric tube or matched placebo (control group) TID for 14 days with optional continuation of treatment up to 21 days, if the patient is still intubated on Day 14. The IMP may be administered orally after extubation and between extubation and day 14 should the patient be able to swallow. In such cases the IMP may be administered either intact or crushed and mixed with a vehicle as per speech swallow evaluation. All patients must receive standard and supportive care according to their clinical status and local guidelines during the whole study period. Although the ventilatory strategy in both groups is in the discretion of the PI, physicians are encouraged to comply with the following ventilator strategy: tidal volume of 4-6 ml/Kg of predicted body weight, a plateau pressure < 30 cm H₂O, driving pressure < 15 cm H₂O to maintain arterial pH > 7.2 and FIO₂/PEEP adjusted to keep SpO₂ $\geq 88\%$ or PaO₂ ≥ 55 mmHg.

Sedation, use of neuromuscular blocking agents or nitric oxide and other inhaled vasodilators, prone positioning, and use of ECMO are left to the PI's discretion and are registered daily on the study's electronic case report form.

Each patient will be involved in the study for up to 60 days. This period consists of informed consent acquisition and screening, randomization and baseline assessments, a post-randomization study period of up to 28 days from the first IMP dose or hospital discharge and a follow-up period of up to day-60. Patients will be assessed daily while hospitalized up to extubation from first IMP administration. The end of this study is defined as the end of follow up.

3.3.1. Rationale for Selection of dose, control group and treatment schedule in the study

The dose and dose regimen have been selected according to the rationale reported in [Section 2.6.3](#).

A double-blind, randomized study design including a placebo group is being adopted as the gold standard to minimize systematic bias and increase baseline comparability between treatment groups. Both groups of patients will receive the current standard of care for ARDS.

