5.2. DOSE, ROUTE AND SCHEDULE OF IMP ADMINISTRATION

Reparixin will be administered through a nasogastric tube at the dose of 1200 mg (2 x 600 mg tablets) TID every 8 hours (6 tablets daily) for 14 days. If the patient becomes extubated prior to the end of treatment on day 14 and if swallowing ability has been restored as per clinical judgment, the IMP can be administered orally. In such cases the IMP may be administered either intact or crushed and mixed with vehicle as per speech swallow recommendation. The IMP may be administered for a total of 21 days if the patient is still intubated on Day 14. Placebo will be administered with the same treatment schedule.

Administration of the study drug through a nasogastric tube should follow this procedure: for each administration, disperse two reparixin 600 mg tablets in 25 mL of drinking water in a suitable container (e.g., conical tubes for 50 mL Falcon centrifuge). Disintegrate the tablets (shaking manually or with the aid of a

planetary shaker or a rocker) until obtaining a homogeneous milky suspension (time required 7–10 minutes). Keep the prepared suspension at room temperature and protected from light for up to 24 hours. Immediately before administration, manually shake the suspension again until complete and homogeneous resuspension, withdraw using a 50 mL needle-free syringe and administer to the patient through the nasogastric tube. After administration, flush the gastric tube with 25 ml of water.

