At days 3 ± 8 h, 7 ± 1 , 14 ± 2 blood samples will be obtained for measurement of the following plasma biomarkers: IL-6, IL-8, PAI-1, TNFr-1, ICAM-1, RAGE

Between extubation and day 28 or hospital discharge (if it occurs before day 28) the following data are collected every 48 ± 8 hours:

- Vital signs: RR, HR, MAP
- PaO₂ (or SpO₂) and FIO₂
- Type of oxygen supportive therapies used if any
- Need for reintubation (after initial extubation)

At day 28 and hospital discharge, the following data will be collected:

- PaO₂ (or SpO₂) and FIO₂
- Type of oxygen supportive therapies used, if any
- Duration of IMV
- ICU length of stay
- Need for reintubation (after initial extubation)
- Hospital length of stay
- Performance of tracheostomy
- Transfer to long term acute care (**LTAC**^{*}) facility

The above information, together with mortality, may be collected by phone follow-up.

^{*}LTAC: An LTAC is a Long Term Acute Care Hospital, i.e., a facility that specializes in the treatment of patients with serious medical conditions, including patients with ongoing needs for mechanical ventilation, but who no longer require intensive care or extensive diagnostic procedures. The patients in LTAC are transferred there directly from the intensive care unit because they require more care than they can receive in a rehabilitation center, skilled care facility or at home.

CCI

CCI

CCI

CCI

CCI

CCI

CCI

CCI

CC

CCI

CCII

CC1

CCI

Safety: The following safety assessments will be performed on day 3 ± 8 h, 7 ± 1 , 14 ± 2 , 21 ± 2 (if reparixin is still administered), 28 ± 2 and at hospital discharge.

- Safety Laboratory Tests (Haematology/biochemistry)
- Estimated Glomerular Filtration rate (eGFR) evaluation
- Hepatic function evaluation up to day 14 or 21, depending on end of treatment
- 12 lead ECG and rhythm analysis

Post-hospital discharge follow-up: on day-60 the patients will be contacted by phone for evaluation of vital status and AEs. Patients will be considered lost to follow up when unable to be contacted upon 3 attempts made on 3 separate days and at 3 separate times.

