9.5.2. Analysis of safety variables

TEAEs and TESAEs will be presented by treatment arms in terms of number of TEAEs and TESAEs and incidence by System Organ Class and Preferred Term using MedDRA. Analyses will be provided also by severity and relationship to the study drug.

Vital signs, hematology and biochemistry, eGFR and ECG parameters will be summarized by treatment at each available time point by means of descriptive statistics.

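### SAP 8.3 stops the by-arm vital-sign tables at first extubation, although vital signs are still recorded afterwards and study drug may continue to Day 14

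*SAP*

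**What the plan says.** **SAP 8.3** sets the cut-off: "Daily assessments through first extubation will be tabulated (considering Study date based on date/time as per section 3.2.1"), and "all the other assessments after extubation will only be listed". **SAP 3.6** words the endpoint similarly: "Vital Signs change from baseline to daily assessment through extubation (namely, day 1, day 2, day 3, day 7, day 14, day 21"). It says extubation where 8.3 says first extubation, so the SAP is not uniform on re-intubated patients.

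**Protocol 9.5.2** is broader: "Vital signs, hematology and biochemistry, eGFR and ECG parameters will be summarized by treatment at each available time point".

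**Collection (Protocol 6.1.3).** Vital signs are recorded daily from Day 1 until extubation, and daily again in any re-intubation period. "Between extubation and day 28 or hospital discharge (if it occurs before day 28) the following data are collected every" 48 ± 8 hours, and that list includes RR, HR and MAP.

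**Exposure.** Protocol 3.3 states: "The IMP may be administered orally after extubation and between extubation and day 14 should the patient be able to swallow". Protocol 5.2 treats extubation before Day 14 as a possible change of route. The stopping criteria in Protocol 5.3.2 do not include extubation, though they do include this one: "The patient is discharged home". Treatment beyond Day 14 is allowed only for patients still intubated on Day 14.

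**The concern.** The cut-off is an event after randomization, and one the drug is meant to bring forward: Protocol 3.1 names liberation from mechanical ventilation among the efficacy aims. A by-arm table at Day 7 or Day 14 limited to patients still in their first intubation does not compare the randomized groups. If reparixin speeds extubation, the two columns hold differently selected patients, and a difference in MAP or RR, or the lack of one, is hard to read.

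The cut-off also removes part of the exposed period. A patient extubated early who goes on taking oral drug adds nothing to the tables after that day. A patient who fails extubation adds nothing during re-intubation, even though daily readings have resumed.

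Laboratory and ECG data (SAP 8.2 and 8.4) are tabulated by time point with no extubation limit. Among the repeated safety measurements, only vital signs are cut in this way.

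**Working it through.** The plan gives no figure to reproduce and no distribution of extubation times. What follows is an illustration under stated assumptions.

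**Inputs from the documents:** a 14-day course; daily readings before extubation and one per 48 h after it (Protocol 6.1.3); about 66 patients enrolled (Protocol 9.1).

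**Assumptions:** 30%, 50% or 70% of patients extubated by Day 14 at a constant daily hazard; extubation at the end of a day; drug then taken to Day 14. Death, discharge, other reasons for stopping drug, and re-intubation are ignored.

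**One patient, first extubation at the end of day x**

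- Untabulated share of treatment days = (14 − x)/14.
- Untabulated readings r(x) = (14 − x)/2, rounded down; share of records = r/(x + r).

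| x | Treatment days | Records |
|---|---|---|
| 4 | 10/14 = 71% | 5/9 = 56% |
| 7 | 7/14 = 50% | 3/10 = 30% |
| 10 | 4/14 = 29% | 2/12 = 17% |

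**Whole trial, proportion p extubated by Day 14**

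- Daily hazard h = 1 − (1 − p)^(1/14).
- P(x) = h(1 − h)^(x − 1) for x = 1 to 14; never extubated by Day 14 = (1 − h)^14.
- Share of days = Σ P(x)(14 − x)/14.
- Share of records = Σ P(x)r(x) / [Σ P(x)(x + r(x)) + 14(1 − h)^14].
- Patients still in the table on day d = 66(1 − h)^d.

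| p | h | Days untabulated | Records untabulated | In table, Day 7 | In table, Day 14 |
|---|---|---|---|---|---|
| 30% | 0.0252 | 15% | 8% | 55 | 46 |
| 50% | 0.0483 | 26% | 14% | 47 | 33 |
| 70% | 0.0824 | 39% | 23% | 36 | 20 |

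The share of records is smaller than the share of days because readings fall from daily to every 48 h. Deaths would reduce the table counts further.

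**What still reaches a by-arm table after first extubation**

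- Heart rate: yes, in part. SAP 8.4 summarizes ECG heart rate and its change from baseline at Days 3, 7, 14 and 21, end of treatment and discharge, with no extubation limit.
- A clinically relevant change in any of the three: yes, as an adverse event (Protocol 8.2), tabulated by arm and study period (SAP 8.1).
- RR and MAP as measurements: no.

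**The case against.** The best defence is that this is a descriptive table in a proof-of-concept trial with no hypotheses, that the restriction is stated openly in SAP 3.6 and 8.3, and that a table held to one ventilatory state is easier to interpret. RR set by a ventilator and RR in a patient breathing unaided are different quantities. Protocol 7.2 does not list vital signs as a safety endpoint at all; the SAP added them. This carries weight. It is a reason to keep the existing table and to separate the two states, but it does not explain why nothing is summarized after first extubation when Protocol 9.5.2 promises more.

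A reader might infer four stronger things that the documents do not support:

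- **That a later drug effect on vital signs cannot appear in any summary.** The ECG heart-rate and adverse-event tables are open to it. All values are listed, and the spaghetti plots in SAP 8.3 are not explicitly cut at extubation.
- **That about half of the on-treatment data is lost.** A median time to extubation of 6 days with exponential times does put 1 − (1 − e^(−14L))/(14L) = 50% of the 14 days after extubation (L = ln 2/6). That is a share of days, not records, and the median has no source in the documents.
- **That the Day 21 table omits on-treatment data for patients extubated by Day 14.** Extension requires intubation on Day 14, so they are off drug by then.
- **That the departure is undeclared.** Two items in SAP 4.11 are redacted, so one can say only that no visible item declares it.

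**Conclusion.** The point holds in a limited form. The SAP's vital-sign tables are narrower than the protocol's commitment. RR and MAP after first extubation have no by-arm numerical summary, and the Day 7 and Day 14 tables are conditioned on an outcome that treatment may change. The size depends on extubation timing, which the documents do not give; the 8% to 23% of scheduled records rests wholly on the assumed 30% to 70% extubated by Day 14 and the simplifications listed. No primary or secondary efficacy endpoint is touched, and no between-arm test of vital signs is planned. Priority: minor.

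**What to change.** - Keep the current SAP 8.3 table, and add by-arm summaries of RR, HR and MAP for all Safety-set patients with a value at Days 2, 3, 7 and 14, regardless of intubation status.
- For Days 7 and 14 use the visit windows (±1 and ±2 days). The 24-hour windows in SAP 3.2.1 would miss roughly half of extubated patients read once per 48 h.
- Show n, an all-patient row, and separate intubated and extubated rows, above all for RR. The separate rows aid interpretation but carry the same selection; the all-patient row is the closer comparison, though still limited to patients alive and in hospital.
- Do not add a Day 28 row: the Day 28 data list in Protocol 6.1.3 contains no vital signs, and collection ends at discharge.
- Add one per-patient summary by arm from first to last dose: lowest MAP, highest HR and highest RR. Give the number of readings per patient beside it, because extremes depend on how often a patient is measured.
- Make SAP 3.6 and 8.3 agree with each other. If the cut-off is kept alone, declare and justify it in SAP 4.11.

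The cost is SAP wording and extra programming, with no new data. The small downside is that the all-patient row mixes ventilatory states, which the separate rows make visible.
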